2.4.2. Multiple Assessments within a visit window

If a subject has multiple assessments on different dates within a visit window the assessment closest to the target visit day will be used for descriptive analysis/plotting, mixed model and response analysis by visits where a single value is associated with a visit.

2.5. Statistical Analysis

2.5.1. Descriptive Analysis

Observed scores and change from baseline will be summarized by treatment group and visit for all 26 subscales. Results will be summarized in a table and figure for each subscale. The tables will include all time points available in the data and the plots are to include time points through cycle 19 (approximately 12.5 months).

2.5.2. Mixed Model Analysis

A mixed model analysis with an outcome of change from baseline and the covariates including baseline score, treatment arm, visit (categorical), treatment arm by time interaction, prior HER2-directed regimens in the metastatic setting (2 or 3+), hormone receptor status (positive or negative), and disease location (visceral and non-visceral) will be used to evaluate differences between treatment arms. The analysis will use the F test from the repeated measures mixed model. Three randomization factors are included in the model to be consistent with the primary analysis as documented in a note to file (dated 8-SEP-2018) to the main SAP.

A reduced mixed model will be used to estimate the change over time by treatment group. These results will be summarized in a table and figure for each subscale. The reduced mixed model will only include baseline score, treatment arm, time (categorical), and treatment arm by time interaction.

2.5.3. Response Analysis

A response analysis will be used to evaluate the score change over time with a minimum clinical important threshold value. At each post-baseline assessment, a subject's score will be classified as having a response of improved, stable, or worsened. A Mantel-Haenszel Chi Square test to assess any differences between treatment arms will be done at each visit and the results will be summarized in a table.

We will conduct the response analysis for the following 7 subscales:

- Global Health
- C30 summary score,
- Physical functioning
- Fatigue

- Constipation
- Diarrhea
- Systemic Therapy Side Effects scale

For the functional scales and the C30 summary score, an improvement is defined as an increase in 10 points or more, worsening is defined as a decrease of 10 points or more, and stable is defined as neither improved nor worsened.

For the symptom scales, an improvement is defined as a decrease of 10 points or more, worsening is defined as an increase of 10 points or more, and stable is defined as neither improved nor worsened. The results will be summarized in a table for each of the seven scales.

2.5.4. Time To Deterioration (TTD) Analysis

For TTD analysis, all records (including multiple assessments within a visit window post baseline assessment) sorted in chronological order will be used to identify the first event. This analysis will be done for the 7 subscales listed in Section 2.5.3

Time to deterioration is defined as the time from Baseline to:

1. Function scales: to the first assessment date where a 10 point or more decrease was observed for the scale of interest
2. Symptom scales: to the first assessment date where a 10 point or more increase was observed for the scale of interest.

If subject's score change did not reach the deterioration threshold value they will be censored at their last HOA assessment. If a subject dies (occurred on or before last dose date plus 28 days) prior to a documented decline in HOA assessment, the subject will be considered to have the deterioration event on the death date unless the date of death occurs after 2 missed HOA assessments (12 weeks + 3 days), in that case, the subject will be censored at last QOL assessment prior to death.

The log-rank test from a Kaplan-Meier method will be used to assess treatment differences. In addition a Cox Proportional Hazards model including treatment arm, prior HER2-directed regimens in the metastatic setting (2 or 3+), hormone receptor status (positive or negative), and disease location (visceral and non-visceral) will be used to estimate the hazard ratio. The use of three of the four randomization strata is documented in a Note to file dated 6-SEP-2018.

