2.5. Treatment Group Assignments or Randomization

Patients will be randomized in a 1:1 ratio to one of the following treatment arms:

- Arm A: neratinib (240 mg) + capecitabine (1,500 mg/m² daily, 750 mg/m² BID)
- Arm B: lapatinib (1250 mg) + capecitabine (2,000 mg/m² daily, 1000 mg/m² BID)

Patient randomization will be stratified according to:

- Number of previous HER2 directed regimens in the metastatic setting (N= 2 or N ≥3).
- Geographic region (North America vs. Europe including Russia and Israel vs. Rest of the World)
- Visceral vs. Non-Visceral only disease
- Estrogen receptor+ (ER+) and/or progesterone receptor (PR+) (i.e., hormone receptor +) versus ER- and PR- (i.e., hormone receptor -).

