2.6. Sample Size Determination

The co-primary endpoints will be analyzed using an overall Type I error rate of 0.01 for PFS and 0.04 for OS. To detect a hazard ratio (experimental vs. control) of 0.70 with approximately 85% power, 419 PFS events (PD/Deaths) are required to be observed; this assumes a median (ITT) PFS of 8.0 months (34.7 weeks) for the experimental arm (neratinib plus capecitabine) and 5.6 months (24.3 weeks) for the control arm (lapatinib plus capecitabine).

It is expected that the 419th event will be observed at approximately 26 months after the first subject is enrolled, which would correspond to approximately half of the death events needed to be observed. At this time, an interim analysis on OS will also be performed. For the OS endpoint, a group sequential method will be employed to maintain the overall Type I error rate at 0.04. Specifically, Lan DeMets alpha spending function approximating the O’Brian-Fleming boundaries will be calculated to create appropriate critical values to which the log rank statistic will be compared (De Mets and Gordon Lan, 1994). If 50% of the deaths are observed at the interim OS analysis, the boundary using the Lan-DeMets alpha spending function is shown in Table 1 for OS interim analysis.

Table 1: Spending Function

Information Fraction	Expected Death Events	Study Month	Boundary (Reject H_0)	2-Sided Significance Level*
50%	185	26	3.066	0.002
100%	378	50	2.058	0.039

* This significance level relates to the 0.04 alpha allocation to OS but will be updated if the entire 0.05 can be allocated to OS.

These boundaries are designed to detect a hazard ratio (experimental vs. control) of 0.725 with approximately 85% power. Overall, 378 OS events (deaths) are required to be observed; this assumes a median (intent to treat [ITT]) OS of 30.3 months for the experimental arm (neratinib plus capecitabine) and 22.0 months for the control arm (lapatinib plus capecitabine).

Approximately 600 subjects will be enrolled and randomized equally between the two treatment arms. This sample size assumes a 1% drop out rate per 12 months (52 weeks) equally distributed between the treatment arms for the PFS endpoint.

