8.3.2. Secondary Efficacy Analyses

The secondary endpoints of ORR, CBR and duration of response will be assessed using the centrally reviewed tumor assessments as well as the investigator tumor assessments. The secondary endpoint of time to intervention for symptomatic CNS disease will only use the investigator-reported data.

The treatment difference in the secondary efficacy endpoint of investigator assessed PFS will be assessed with the product limit estimate of the median time to event. Differences between treatment groups will be examined using a log rank test statistic stratified by hormone receptor status, number of prior HER2-directed regimen in the metastatic setting, visceral disease status, and geographic region strata (similar to the analyses for the primary endpoints). All time-to-event endpoints including time to intervention for symptomatic CNS disease will be displayed using a Kaplan-Meier survival plot.

For the secondary endpoints of ORR and CBR the subjects included in the analyses are those that had measurable disease (per RECIST v1.1) at screening. Any tumor assessments after the start of new anti-cancer therapy will not be included in the analyses for these two endpoints. The treatment difference in the secondary efficacy endpoints of ORR and CBR will be analyzed using a Cochran-Mantel-Haenzel (CMH) Chi-square test, stratified on hormone receptor status, number of prior HER2-directed regimens in the metastatic setting, geographic region and disease category (visceral vs. non-visceral only).

Duration of response will be summarized by treatment group for the patients that responded. If there are patients that continue to respond, they will be censored at their last tumor assessment and a Kaplan-Meier analysis will be done to estimate the duration of response.

With the exception of the CNS endpoint, which will be tested only after the null hypothesis is rejected for OS; all other secondary endpoints are descriptive analyses and will be done at the time of the primary PFS analysis.

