2.5.5. Area Under Curve (AUC) analysis

Time adjusted AUC will be derived for each of the subscales listed in Section 2.5.3

The time adjusted AUC is calculated using the trapezoidal rule between adjacent time points using the actual assessment study day for each subject by subscale. This method sums up the areas cumulated through multiple consecutive time point assessments from baseline assessment day to last assessment day. The area between two time points is calculated by taking the average subscale score between the 2 time points and multiplied by the duration between the two time points.

All assessments post baseline will be utilized except when there are multiple assessments on the same day, in which case, only the derived average subscale for the day in question will be used.

Time-adjusted area under the curve = Area under the Curve/(duration from baseline assessment to last assessment in days)

Comparison of AUC by treatment group will be summarized in a table using an ANCOVA model to test for treatment difference of AUC. The model will include the baseline subscale value and treatment arm.

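### Several descriptive QoL analyses in the supplemental SAP leave out the randomisation factors that the QoL mixed-model F test and time-to-deterioration Cox model use

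*SAP*

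**What the plan says.** Main SAP 2.5: "Patient randomization will be stratified according to" four factors, namely number of prior HER2-directed regimens, geographic region, visceral disease and hormone receptor status. Allocation is 1:1.

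Elsewhere the plan stratifies its between-arm tests and says so. Main SAP 8.3.2, on investigator-assessed PFS: "Differences between treatment groups will be examined using a log rank test statistic stratified by hormone receptor status", followed by the other factors. The same section stratifies the CMH tests for ORR and CBR. Supplemental SAP 3.3 specifies stratified log-rank tests for the CNS analyses.

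The QoL part of the supplemental SAP is mixed:

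- **2.5.2, full mixed model (F test):** includes prior regimens, hormone receptor status and disease location, for consistency with the primary analysis, citing a note to file.
- **2.5.2, by-visit estimates:** "The reduced mixed model will only include baseline score, treatment arm, time (categorical), and treatment arm by time interaction".
- **2.5.3, response:** "A Mantel-Haenszel Chi Square test to assess any differences between treatment arms will be done at each visit". No strata are named.
- **2.5.4, TTD test:** "The log-rank test from a Kaplan-Meier method will be used to assess treatment differences". No strata are named. The Cox model in the next sentence has the three factors as covariates.
- **2.5.5, AUC ANCOVA:** "The model will include the baseline subscale value and treatment arm".

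Main SAP 8.3 and 8.3.2 make every secondary endpoint other than CNS intervention descriptive.

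**The concern.** When patients are randomised within strata, prognostic factors are balanced between arms by design. An analysis that ignores them still counts their variation as noise. Its standard error is then too large for the design: the test rejects less often than its nominal level under the null and has less power under an alternative.

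The plan is also inconsistent with itself. Supplemental SAP 2.5.2 gives a reason for including the factors and, in the next paragraph, drops them from the by-visit estimates without giving one. In 2.5.4 the p-value comes from a test with no stated strata and the hazard ratio from an adjusted model, so the two can point different ways near 0.05. Health outcomes are a named secondary objective of an open-label trial. A conservative comparison can hide harm as well as benefit, for example on the diarrhea scale.

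**Working it through.** The plan gives no QoL sample size, effect, variance or alpha, so there is no QoL figure to reproduce. The check is a comparison of the text, followed by a size calculation on assumed inputs.

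**Text**

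| Analysis (supplemental SAP) | Stratification factors |
|---|---|
| Mixed-model F test, 2.5.2 | three, stated |
| Reduced mixed model, 2.5.2 | explicitly none |
| Response test, 2.5.3 | none named |
| TTD log-rank, 2.5.4 | none named |
| TTD Cox hazard ratio, 2.5.4 | three, as covariates |
| AUC ANCOVA, 2.5.5 | explicitly none |

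**TTD log-rank test**

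The statistic is Z = U/√V, with U = Σ(a − p) and V = Σp(1 − p) over events. Here a is the arm indicator and p the proportion of those at risk who are in that arm. The stratified version computes U and V within each stratum and adds them.

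Assumptions common to both sets: three binary factors with prevalence 0.3, 0.6 and 0.8 (8 strata); permuted blocks of 4 within strata; treatment hazard ratio 0.72; two-sided 0.05; 3,000 trials per cell. The Monte Carlo SE is about 0.8 points for power and 0.4 for the null.

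Set A: 560 patients, control TTD median 6 months, exponential censoring with medians 8.0 and 5.6 months (the planned PFS medians in main SAP 2.6).

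| Factor HRs | Power unstratified / stratified | Null rejection unstratified / stratified |
|---|---|---|
| 1.2, 1.2, 1.2 | 76.0% / 74.8% | 5.4% / 5.2% |
| 1.3, 1.5, 1.4 | 75.5% / 76.0% | 4.2% / 4.5% |
| 1.5, 1.8, 1.6 | 72.1% / 75.0% | 3.8% / 4.9% |
| 1.5, 2.2, 2.0 | 69.9% / 76.0% | 3.6% / 5.3% |

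Set B: 500 patients, median 6 months for control patients with no factor present, censoring median 8 months in both arms, the same HR for each factor.

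| HR per factor | Power unstratified / stratified | Null rejection unstratified / stratified |
|---|---|---|
| 1.0 | 75.9% / 74.7% | 5.8% / 5.8% |
| 1.2 | 79.2% / 77.9% | 4.9% / 4.9% |
| 1.5 | 81.6% / 84.3% | 4.1% / 4.8% |
| 2.0 | 80.3% / 88.2% | 3.2% / 5.2% |

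The loss with clearly prognostic factors is 75.0 − 72.1 = 2.9 and 76.0 − 69.9 = 6.1 points in set A, and 84.3 − 81.6 = 2.7 and 88.2 − 80.3 = 7.9 points in set B. With moderate factors (set A, second row) it is 0.5 points, inside simulation error. With weak factors there is no loss. The two tests fall on opposite sides of 0.05 in 6 to 10% of set A trials.

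**AUC ANCOVA**

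If the factors explain a share R² of the variance left after baseline, adjustment multiplies the SE by √(1 − R²). For R² of 2% and 8% this is √0.98 = 0.990 and √0.92 = 0.959, so the SE is 1 to 4% smaller. Take 250 per arm and an effect giving 80% power unadjusted, so that 1.960 + 0.842 = 2.802 SEs. At R² = 10%, 2.802/√0.90 = 2.953, and 2.953 − 1.960 = 0.993 gives 84.0% power. R² of 1%, 2% and 5% gives 80.4%, 80.8% and 82.0%.

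**Late-visit response tests**

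QoL forms stop with study drug (supplemental SAP section 2). Take the planned PFS medians as a proxy for time on drug. Cycle 19 Day 1 is Day 379, and 378/30.44 = 12.4 months. Expected on drug: 300 × 2^(−12.42/8.0) + 300 × 2^(−12.42/5.6) = 102 + 64 ≈ 167 of 600. With the assumed prevalences the smallest stratum holds 0.3 × 0.4 × 0.2 = 0.024 of them, about 4 patients across both arms.

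**The case against.** The strongest reply is that nothing inferential depends on this. The QoL tests carry no alpha. The mixed model, which is the only between-arm QoL analysis specified in the protocol and main SAP, is already adjusted, and so is the TTD hazard ratio. All of that stands, and it limits how much the point matters.

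Three further points stand in part:

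- For the log-rank and response tests the omission is read from silence, and the plan uses the word stratified loosely: the Cox model without competing events for progressive CNS lesions is called stratified in supplemental SAP 3.3.2 but not in main SAP 8.3.2. The note to file cited in 2.5.4 is not available to check. But 2.5.4 names three factors for the Cox model directly after a log-rank sentence with none, so the text needs an edit whichever was meant.
- The reduced model is described as estimating change over time, not testing, and its tables are listed separately from the F-test tables. Unadjusted means are a legitimate display. What is missing is a label, and adjusted means to go with the adjusted test.
- The response and AUC analyses have no adjusted counterpart of their own. Their mismatch is with the other QoL models.

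A reader might infer that the QoL p-values are anti-conservative, or that the trial's conclusions lose power. The documents support neither: the simulated error is conservative and no conclusion is gated on these tests. A reader might also infer that stratifying the log-rank test alone would bring the TTD p-value and hazard ratio into line. It would not, because the Cox model in 2.5.4 enters the factors as covariates, and a stratified log-rank test corresponds to a stratified Cox model.

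**Conclusion.** The point holds as an inexpensive improvement to descriptive analyses. The omission is explicit for the AUC ANCOVA and the reduced mixed model, and probable for the TTD log-rank and response tests. No alpha or confirmatory result is affected.

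For the TTD test, the unstratified version loses 2.7 to 7.9 power points, with null rejection of 3.2 to 4.1%, if the three factors have hazard ratios of about 1.5 to 2 each for QoL deterioration. It loses nothing measurable if they are weak. For the AUC analysis the gain from adjustment is 0.4 to 4 points for a residual R² of 1 to 10%. The effect on the response test was not simulated. Prognostic strengths, prevalences, block size, QoL population size, TTD median and treatment effect are all assumptions, because the documents give none of them for QoL.

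**What to change.** In supplemental SAP 2.5, use the three factors of the final primary analysis throughout:

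1. **AUC (2.5.5):** add them as covariates to the ANCOVA.
2. **TTD (2.5.4):** use a stratified log-rank test and take the hazard ratio from a Cox model stratified by the same factors, so that the p-value and hazard ratio agree.
3. **Response (2.5.3):** use a CMH row-mean-score test on improved, stable and worsened, stratified by the same factors. State that sparse strata at late visits, including any with patients from one arm only, will contribute little or nothing. The test remains valid.
4. **By-visit estimates (2.5.2):** report least-squares means from the full mixed model used for the F test. Reduced-model means may stay if labelled unadjusted and descriptive.

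If unadjusted versions are intended anywhere, say so, give the reason, and label the outputs. While editing, reconcile the date of the note to file on the strata, given as 8 September 2018 in 2.5.2 and 6 September 2018 in 2.5.4.

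The cost is SAP wording and a few program lines. The factors are already collected and already used in the other QoL models, so no new data are needed.

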2.5.5. Area Under Curve (AUC) analysis

Time adjusted AUC will be derived for each of the subscales listed in Section 2.5.3

The time adjusted AUC is calculated using the trapezoidal rule between adjacent time points using the actual assessment study day for each subject by subscale. This method sums up the areas cumulated through multiple consecutive time point assessments from baseline assessment day to last assessment day. The area between two time points is calculated by taking the average subscale score between the 2 time points and multiplied by the duration between the two time points.

All assessments post baseline will be utilized except when there are multiple assessments on the same day, in which case, only the derived average subscale for the day in question will be used.

Time-adjusted area under the curve = Area under the Curve/(duration from baseline assessment to last assessment in days)

Comparison of AUC by treatment group will be summarized in a table using an ANCOVA model to test for treatment difference of AUC. The model will include the baseline subscale value and treatment arm.

2.5.6. Completion rate

A completion analysis will be done to evaluate the magnitude of missing assessments. The completion analysis will focus on the following scales.

1. QLQ-C30 – the C30 summary subscale (required non-missing subscale scores from all except financial difficulty, the most conservative scale from C30)
2. BR-23 - the systemic therapy sides effects subscale
3. EQ5D-5L - either the VAS or Index Score

Completion is defined as:

- Overall: The actual number of assessments (baseline and all post baseline assessments) / expected number of assessments (from baseline to last assessment thru last dose date+28 days)*100%.
- Calculation for expected number of assessments will be based on treatment duration and corresponding cycle of last dose day. If last dose day falls in a day in cycle Y which is the completion of an even cycle , the expected number of HOA assessments will be the integer part of $(Y/2) + 1$; or else If last dose day falls in a cycle Y and $Y/2$ does not yield a whole number then , the expected number of HOA assessments will be the integer portion of $(Y/2) + 2$.

For example, a subject with the last dose in cycle 4 would be expected to have 3 assessments (Baseline, cycle 3 and EOT). If there are multiple assessments on the same day only one assessment will be counted for that day. Lastly, if the completion is greater than 100%, it will be truncated at 100%.

- Completion at each scheduled visit: The number of subjects that completed the scale flagged for the scheduled visit divided by the number of subjects under treatment in the corresponding cycle.

The overall completion rate and completion rate by visit will be summarized by treatment group for each relevant scale.

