4. ANALYSIS POPULATIONS

Four analysis populations will be used for this study: the Intent to treat (ITT) population, the Safety Population, the Pharmacokinetics (PK) population and the Quality of Life population (QoL).

The analysis of the primary and secondary efficacy endpoints will be performed using the ITT population. All safety analyses will be performed using the Safety Population. Exploratory Pharmacokinetics analyses will be performed using the PK population. Quality of life analyses will be performed using the QoL population.

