4.4. Quality of Life (QoL) Population

The QoL population consists of all patients in the safety population for whom a baseline and at least one post baseline Health Outcomes Assessment (HOA) are available.

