1. INTRODUCTION

This supplemental Statistical Analysis Plan (SAP) is intended to further describe the efficacy analysis for the secondary endpoints of Health Outcomes Assessments (HOA) and Central Nervous System (CNS) as well as some additional sensitivity analyses.

For the purposes of this supplemental SAP we will use the term Quality of Life (QoL) to cover all the analysis relating to the Health Outcomes Assessments (HOA).

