2.1.1. QoL populations

In the 1301 SAP version 2.1 the QoL population was defined as a single population across all the HOA instruments. After the approval of the SAP it was determined that it would be best to define a separate population for each of the subscales. A subject will be included in the population for a particular subscale if they are in the safety population and they had a baseline assessment for that subscale as well as at least one post baseline assessment (up to last dose day +28 days) for the specific subscale. In the analysis dataset there will be a flag for each subscale population.

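### Under the default QoL population rule, the overall completion rate in Supplemental SAP 2.5.6 leaves out treated patients with no baseline or no later form, and cannot fall below 100% for patients whose last dose is in cycle 1 or 2

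*SAP*

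**What the plan says.** - **Main SAP, section 4:** "Quality of life analyses will be performed using the QoL population". Section 4.4 limits that population to safety-population patients "for whom a baseline and at least one post baseline Health Outcomes Assessment (HOA) are available".
- **Supplemental SAP, section 1:** the term QoL covers every analysis of the health outcomes assessments. Completion is one of these and sits in section 2 with the others.
- **Supplemental SAP 2.1.1:** the single QoL population is replaced by one per subscale. A patient must be in the safety population and have a baseline form "as well as at least one post baseline assessment (up to last dose day +28 days) for the specific subscale".
- **Supplemental SAP 2.5.6:** "A completion analysis will be done to evaluate the magnitude of missing assessments". It defines two rates. The overall rate is forms returned divided by forms expected, with the expected number taken from the cycle of last dose and the result capped at 100%; no population is named. The by-visit rate is patients with a form flagged to that visit, divided by patients on treatment in that cycle.
- **Supplemental SAP 2.5.7:** a pattern mixture or similar analysis may be added ad hoc after review of the descriptive results and the completion rates.

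**The concern.** A completion rate is there to show how much is missing. Under the default rule, entry to the population depends on having returned forms, so the patients with the most missing data never reach the calculation. The effect is greatest in patients who stop within the first two cycles, where stopping for toxicity or progression makes missing questionnaires most likely to be informative. Health outcomes are a secondary objective of an open-label trial, and Protocol 7.1.1 names diarrhea, with early onset, as neratinib's major dose-limiting toxicity. A rate that cannot fall below 100% in this group would give false reassurance about the QoL comparison. Neither list of planned tables (main SAP section 12, Supplemental SAP Table 2) includes QoL-population exclusions by arm, so the loss would be hard to see.

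**Working it through.** **1. Expected forms, from the plan's own rule.** For last dose in cycle Y, E(Y) = int(Y/2) + 1 if Y is even and int(Y/2) + 2 if Y is odd. E(4) = 3, which reproduces the worked example in 2.5.6.

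**2. Lowest possible score for an included patient.** Membership requires a baseline form on or before first dose and another after it (2.4.1), so at least two forms on different dates. The floor is min(1, 2/E).

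| Cycle of last dose | Forms expected | Floor if included | Possible scores below the floor, all treated |
|---|---|---|---|
| 1-2 | 2 | 100% | 0%, 50% |
| 3-4 | 3 | 66.7% | 0%, 33.3% |
| 5-6 | 4 | 50% | 0%, 25% |
| 7-8 | 5 | 40% | 0%, 20% |

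The 100% result is exact for cycles 1-2 and for no later cycle.

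**3. Does the by-visit rate fill the gap?** Its first post-baseline visit is Cycle 3 Day 1, and the window table in 2.4.1 has no end-of-treatment row. A patient who stopped in cycle 1 or 2 is not on treatment in cycle 3, so a missing end-of-treatment form does not count against that rate.

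**4. Size.** Inputs: planned PFS medians of 8.0 and 5.6 months (main SAP 2.6). Assumptions: exponential time on treatment with those medians; each post-baseline form completed independently with probability p; baseline completed with probability b; overall rate taken as the mean of per-patient rates.

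- Share with k expected forms: w(k) = exp(-42λ(k-2)) - exp(-42λ(k-1)), where λ = ln 2/(30.44 × median). For k = 2 this is 11.3% (8.0 months) and 15.7% (5.6 months).
- Probability of inclusion: b[1 - (1-p)^(k-1)].
- Mean rate if included: [1 + (k-1)p/(1 - (1-p)^(k-1))]/k. At p = 0.8: 100% (k = 2), 88.9% (k = 3), 85.5% (k = 4).
- Mean rate in all treated: [b + (k-1)p]/k. At p = 0.8, b = 1: 90%, 86.7%, 85%.

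Weighted over k (neratinib / lapatinib):

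| p | b | Rate as reported | Rate in all treated | Excess, points | Left out |
|---|---|---|---|---|---|
| 0.9 | 1 | 92.4 / 93.0% | 91.9 / 92.2% | 0.5 / 0.8 | 1.2 / 1.7% |
| 0.8 | 1 | 84.8 / 85.9% | 83.7 / 84.5% | 1.0 / 1.5 | 2.7 / 3.8% |
| 0.7 | 1 | 77.0 / 78.8% | 75.6 / 76.7% | 1.5 / 2.1 | 4.6 / 6.3% |
| 0.9 | 0.9 | 92.4 / 93.0% | 90% | 2.4 / 3.0 | 11.1 / 11.5% |
| 0.8 | 0.8 | 84.8 / 85.9% | 80% | 4.8 / 5.9 | 22.2 / 23.0% |
| 0.7 | 0.7 | 77.0 / 78.8% | 70% | 7.0 / 8.8 | 33.2 / 34.4% |

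The reported rate does not depend on b: missing baseline forms remove patients without changing the figure shown.

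**5. If early stoppers return fewer forms than others.** Illustration, all rates assumed: 300 treated in an arm, 15% (45) stop in cycles 1-2, half of those return only the baseline form, and later stoppers complete 85%. All treated: (22.5 + 22.5 × 0.5 + 255 × 0.85)/300 = 83.5%. QoL population: (22.5 + 255 × 0.85)/277.5 = 86.2%. Among the early stoppers it is 75% against a fixed 100%.

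**The case against.** **The population is inferred.** 2.5.6 does not itself say that the overall rate is run in the QoL populations. The expected count rests on treatment duration, which exists for every dosed patient, and for EQ-5D-5L either of two scores is accepted, which matches no single per-subscale population. An all-treated reading is therefore possible. This stands as evidence that the text is unclear. It does not displace the default, because no exception is written.

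**The by-visit rate already uses treated patients.** This is right on a literal reading. A reader might infer that it is inflated in the same way, but its stated denominator does not support that. It still does not repair the overall rate, for the reason in step 3 of the working.

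**Baseline forms should seldom be missing.** Protocol 9.1 and Appendix 1 require baseline health outcomes within 72 hours before randomization, and randomization is to follow completed baseline assessments. This stands, and it makes the b = 1 rows the more plausible end.

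**Missing-data analysis does not hang on this rate.** A reader might infer that the completion rates decide whether any sensitivity analysis is done. They do not: main SAP 8.3.3.2 already plans pattern mixture models, and 2.5.7 concerns additional work, also informed by the descriptive results.

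**The stakes are limited.** QoL tests are descriptive (main SAP 8.3), and the per-subscale flags would let population sizes be compared with the safety population. Both are true, and they keep this a modest point.

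**Conclusion.** The point holds for the overall rate under the default population rule. As written, that rate omits treated patients with no baseline or no post-baseline form, and it is 100% by construction for included patients whose last dose is in cycle 1 or 2. It would be too broad to say this of early-stopping patients in general, since a lower score is possible from cycle 3 on.

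The bias is upward and largest among early stoppers. At p = 0.8 with time on treatment following the planned PFS medians, it is about 1.0 to 1.5 points with 3-4% of treated patients left out if baseline is always completed, rising to 5 to 6 points with 22-23% left out if baseline is completed only 80% of the time. The upper figures should not be quoted alone, because they depend on baseline forms being missing as often as later ones. All these sizes rest on assumed completion rates; the documents give none. Independence is also assumed, and step 5 of the working shows a larger gap when early stoppers return fewer forms.

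**What to change.** In Supplemental SAP 2.5.6:

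1. State that the overall rate is computed in all treated patients (safety population), counting expected forms whether or not any form was returned.
2. Confirm that the by-visit denominator is all treated patients still on treatment in that cycle, with no QoL-population restriction.
3. Add a table, by arm, of the treated patients excluded from each QoL population, split into no baseline form and no post-baseline form.

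The cost is one sentence, one changed denominator and one table, with no new data collection. Reported completion becomes slightly less favourable.
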